With respect to sample size for aim 1, by Lehr's approximation, a sample size of 16 would be needed to identify a 1 standard deviation difference in the mean score on the Medication Treatment Satisfaction Questionnaire. The target sample size is 20 patients to account for possible patient dropout. With respect to sample size for aim 2, by Lehr's approximation, a sample size of 20 provides 95% confidence intervals of approximated +/- 20% around most reported percentages. If the reported rate of success in increasing metformin dose is 30%, the 95% confidence interval around that estimate will range from 10% to 50%. If the reported percentage is 0%, the 95% confidence interval will be approximately 0-15%. We think these are sufficiently precise estimates to help clinicians decide whether n-of-1 clinical trials are a useful intervention for overcoming metformin intolerance.

Inclusion/ Exclusion Criteria:

Patients will be eligible if they are between the ages of 18 and 100. Patients will be recruited in an outpatient setting. Subjects will be enrolled regardless of gender, though a 50:50 ratio of male to female subjects is desirable.

Patients will be ineligible if they have a contraindication to metformin (ie, advanced renal or liver disease, a history of lactic acidosis attributed to metformin, or advanced heart failure). Pregnant women will be excluded from this study due to risk of confounding; pregnant women frequently have nausea and vomiting, changing over time, which if included may invalidate the results of the study.

Assessing Safety and Efficacy:

No data will be collected systematically to monitor safety or efficacy, only tolerability. However, the gastrointestinal symptom questionnaire will serve to quantify gastrointestinal adverse events every 2 weeks. Patients will be educated on potential side effects and risks of metformin and encouraged to both stop the medication and contact the investigators if they experience intolerable side effects or any severe adverse reactions.

Interim and Complete Stopping Rules:

Due to the small sample size, short duration, and limited risks of this study, statistical stopping rules are not specified. Patients are encouraged to speak with their physicians and study coordinators regarding any medication-associated adverse events that may occur as a result of participation in this study.

Adverse Events Collection:

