Adverse events that may cause termination or dropout of a subject include hypoglycemia, lactic acidosis, and severe gastrointestinal effects including severe nausea, vomiting, and diarrhea.

Metformin has a well-established safety profile in this clinical setting and no active monitoring for adverse events is planned. Patients who are using diabetes drugs associated with hypoglycemia (sulfonylurea, insulin, or meglitinide) will be advised of the potential for metformin to increase risk of hypoglycemia by potentiating the action of those drugs, and to immediately report any occurrence of hypoglycemia both to the study team and to their regular physician

Adverse events will be graded according to the "Common Terminology Criteria for Adverse Events (CTCAE) v4.0" scale produced by the United States Department of Health and Human Services and the National Institutes of Health. The CTCAE scale rates potential adverse events on a scale from 1 to 5, and is a commonly accepted method of grading adverse events. All adverse events will be recorded on the Office of Research Integrity's "Adverse Event & IND Safety Reporting Cumulative Table". We will report all required adverse events and incidents to NYPH-WCM Patient Services, Risk Management, and/or the Department of Health.

In addition to the IRB, all adverse events recorded during this trial will be reported to [name], and [name].

¹ Joy TR, Monjed A, Zou GY, Hegele RA, McDonald CG, Mahon JL. N-of-1 (Single-Patient) Trials for Statin-Related Myalgia. *Annals of Internal Medicine*. 2014;160(5):301-310

² Salpeter SR, Greyber E, Pasternak GA, Salpeter EE. Risk of fatal and nonfatal lactic acidosis with metformin use in type 2 diabetes mellitus. *Cochrane Database Syst Rev*. 2010;2010(4):Cd002967.

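### All adverse events are to be recorded and graded, but only gastrointestinal ones are asked about; hypoglycaemia and other events depend on the patient coming forward

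*Combined protocol and SAP*

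**What the plan says.** Two sections of the combined protocol and SAP bear on this.

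Assessing Safety and Efficacy states: "No data will be collected systematically to monitor safety or efficacy, only tolerability". It makes one exception: "the gastrointestinal symptom questionnaire will serve to quantify gastrointestinal adverse events every 2 weeks".

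Adverse Events Collection refers to metformin's established safety record and states that "no active monitoring for adverse events is planned". The same section says that events will be graded by CTCAE v4.0, on a scale that starts at grade 1, and "All adverse events will be recorded on the Office of Research Integrity"'s cumulative table. It lists hypoglycaemia and lactic acidosis, with severe gastrointestinal effects, as events that may end a patient's participation. Patients taking sulfonylurea, insulin or meglitinide are to be "advised of the potential for metformin to increase risk of hypoglycemia by potentiating the action of those drugs", and are told "to immediately report any occurrence of hypoglycemia both to the study team and to their regular physician".

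The Study Overview schedules questionnaires at the end of each two-week period and names their topics as satisfaction, gastrointestinal symptoms and adherence. No section describes a general health question or a hypoglycaemia question.

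**The concern.** The plan promises a complete, graded record of adverse events and also declares that it will not go looking for them. Outside the gastrointestinal questionnaire, an event is recorded only if the patient decides that it is worth mentioning. The Relevant Scientific Background section describes patients whose complaint is a vague malaise, and the Study Overview speaks of side effects beyond gastrointestinal ones. These are the complaints least likely to be volunteered consistently.

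What is at stake is the completeness of the safety record. If the final table shows few or no non-gastrointestinal events, a reader cannot tell whether they did not occur or were not reported. This matters most for hypoglycaemia, which the plan itself names as a risk with certain background drugs. The means of asking is already in place, because each patient completes a form every two weeks.

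**Working it through.** The plan gives no figure for event ascertainment, so the main check is to follow each kind of event to the table.

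**Routes described in the plan**

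- *Gastrointestinal events:* solicited by questionnaire every two weeks (Assessing Safety and Efficacy). No gap.
- *Hypoglycaemia, users of the three named drug classes:* the patient is warned in advance and told to report any occurrence immediately (Adverse Events Collection). There is no severity threshold, but the report must start with the patient.
- *Hypoglycaemia, all other patients:* no specific instruction is described beyond general education on side effects and risks.
- *Other events the patient finds intolerable or severe:* the patient is encouraged to contact the investigators (Assessing Safety and Efficacy).
- *Other events the patient links to the medication:* the patient is encouraged to speak with physicians and coordinators (Interim and Complete Stopping Rules).
- *Mild events the patient does not link to the medication:* no route is described.

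For non-gastrointestinal events other than hypoglycaemia, then, the patient must first judge severity or cause, and does so while blinded. The recording commitment carries neither filter: it covers all events, and the grading scale begins at grade 1.

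**Opportunities to ask**

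There are four metformin blocks separated by placebo blocks, with the first treatment randomised. That gives three or four placebo blocks, so 7 or 8 two-week questionnaires per patient. With 20 patients and no dropout, 20 × 7 = 140 or 20 × 8 = 160 completed forms. This counts opportunities to ask, not missed events.

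**What incomplete reporting would do (illustration; event rates and reporting shares are assumed)**

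Let p be the proportion of patients who have a given event and c the share of those events that is reported. With n = 20, the chance of recording at least one is 1 − (1 − p·c)^20.

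| p | c = 1 | c = 0.5 | c = 0.25 |
|---|---|---|---|
| 10% | 0.88 | 0.64 | 0.40 |
| 5% | 0.64 | 0.40 | 0.22 |
| 2% | 0.33 | 0.18 | 0.10 |

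For example, 1 − 0.90^20 = 0.88 and 1 − 0.95^20 = 0.64.

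The Statistical Considerations section gives an upper confidence limit of about 15% when nothing is observed in 20 patients. It does so for aim 2, but the arithmetic is the same for an adverse event: the rule of three gives 3/20 = 0.15, which reproduces the figure. That limit assumes full ascertainment. If only a share c is reported, zero recorded events limits p·c to 0.15, so p could be as high as 0.15/c: 0.15/0.5 = 30%, or 0.15/0.25 = 60%.

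**The case against.** The strongest defence is that this is a declared and reasoned choice for a small trial of a marketed drug. The plan says that metformin's adverse events are mainly gastrointestinal, and those are solicited. It describes the hypoglycaemia risk of metformin as near zero, with a caveat for concomitant agents. It excludes patients with contraindications and educates those enrolled. This justifies light monitoring. It does not explain why a risk named in the plan is left off the topics of a form that patients already complete.

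Four stronger readings are tempting, and the documents do not support them.

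- *A reader might infer that the plan contradicts itself outright.* Passive surveillance, in which every event that reaches the team is recorded and graded, is a coherent reading. But the plan does not state that limit, and even on that reading it gives no means of finding the rest.
- *A reader might infer that hypoglycaemia reporting is purely spontaneous.* It is not for users of the three named drug classes, who have a directed instruction. Immediate reporting is also faster than a two-weekly question, which can add to it but not replace it.
- *A reader might infer that trial results will be biased, because beliefs about treatment drive reports.* The Primary and Secondary Objectives cover satisfaction, gastrointestinal scores, adherence, the treatment guess and six-month tolerance. No comparison of non-gastrointestinal events is planned, so no planned result is affected. A standard question would not remove belief-driven reporting either.
- *A reader might put a figure on the share of events missed, or conclude that the forms certainly omit the question.* The documents give no reporting rate. The forms are not reproduced, and the Study Overview's list of topics is not exhaustive, since it leaves out the treatment-guess question that the Secondary Objectives require. All that can be said is that no such item is described.

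**Conclusion.** The point holds as a gap in ascertainment. The plan adopts a policy of not asking about non-gastrointestinal events while undertaking to record and grade all events. As described, mild or unattributed non-gastrointestinal events have no assured route to the table, and hypoglycaemia depends on the patient's initiative. The record would be incomplete by an unknown amount, and a recorded zero would not carry the reassurance of the 15% limit. The probabilities and wider limits shown above rest on assumed rates and indicate direction only.

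The sample size, the primary and secondary analyses and the tolerability conclusions are untouched. The change is worth making because it improves safety ascertainment at very little cost, but the trial's main results do not depend on it.

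**What to change.** 1. Add two standard questions to each two-weekly questionnaire, identical in every block: one open question on any health problem since the last contact, and one on low-blood-sugar episodes. Place them after the satisfaction and gastrointestinal items so that they do not influence those answers.
2. Keep the existing instruction on immediate reporting of hypoglycaemia.
3. In Adverse Events Collection, replace "no active monitoring for adverse events is planned" with: *adverse events are solicited at each two-weekly questionnaire and otherwise recorded when reported*. Amend the statement in Assessing Safety and Efficacy that excludes systematic safety data, so that the two sections agree.
4. Tabulate events descriptively by metformin and placebo block, with the number of completed blocks as denominator, since a patient may have four metformin blocks and only three placebo blocks. No test is needed.

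The cost is two questions on an existing form, one table and the two text changes, with no added visits or tests. The downsides are more minor events to log and grade, and some possible prompting of symptoms. The prompting applies equally in metformin and placebo blocks.
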